15 DISCONTINUATION AND REPLACEMENT OF SUBJECTS

15.1 Early Discontinuation

A subject may be discontinued from study treatment at any time if the subject's legal guardians or the Investigators feel that it is not in the subject's best interest to continue. The following is a list of possible reasons for study treatment discontinuation:

- Subject withdrawal of consent
- Subject is not compliant with study procedures
- Adverse event that in the opinion of the investigator would be in the best interest of the subject to discontinue study treatment
- Protocol violation requiring discontinuation of study treatment

- Lost to follow-up
- Sponsor request for early termination of study

If a subject is withdrawn from treatment due to an AE, the subject will be followed and treated by the Investigator until the abnormal parameter or symptom has resolved or stabilized.

15.2 Withdrawal of Subjects from the Study

A subject may be withdrawn from the study at any time if the subject, the investigator, or the Sponsor feels that it is not in the subject's best interest to continue.

All subjects are free to withdraw from participation at any time, for any reason, specified or unspecified, and without prejudice.

Reasonable attempts will be made by the investigator to provide a reason for subject withdrawals. The reason for the subject's withdrawal from the study will be specified in the subject's source documents.

15.3 Replacement of Subjects

Subjects who withdraw from the study prior to the recording of the MRI images required for statistical analyses will be replaced.

16 PROTOCOL VIOLATIONS

A protocol violation occurs when the subject, investigator, or Sponsor fails to adhere to significant protocol requirements affecting the inclusion, exclusion, subject safety and primary endpoint criteria. Protocol violations for this study include, but are not limited to, the following:

- Failure to meet inclusion/exclusion criteria

Failure to comply with Good Clinical Practice (GCP) guidelines will also result in a protocol violation. The Sponsor will determine if a protocol violation will result in withdrawal of a subject.

17 DATA SAFETY MONITORING

A Data Monitoring Committee (DMC) will review data relating to safety and efficacy, will conduct and review interim analyses, and will ensure the continued scientific validity and merit of the study, according to the UCLA Data Safety Monitoring Board Operations Manual. There will be at least 3 members, who will have no other role in the trial, including at least one expert with statistical expertise, one member with clinical specialty of pediatric cardiology, and one member with experience serving on independent data review boards. At the first meeting, held before the trial either face-to-face or via tele-conference, the committee will approve or revise the charter. The chair of the DMC will be appointed by the PI of the study.

18 STATISTICAL METHODS AND CONSIDERATIONS

The primary efficacy analysis of visual imaging quality will be conducted using all usable scans from the patients. All safety analyses will be conducted using a population defined as all patients undergoing study contrast-agent (Safety Population).

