7.2 Study Design Part I: diagnostic efficacy of Feraheme vs. Ablavar

For Part I of our study, the legal guardian(s) of all consecutive pediatric patients with suspected or known CHD referred for cardiovascular MRI will be given the option of having their child undergoing an Ablavar®-enhanced MRI or a Feraheme®-enhanced MRI, after the potential benefits and risks of both agents are clearly explained and their questions addressed. The risks and benefits of using each of these agents will be verbally discussed with the patients' legal guardians and referring cardiologists or cardiac surgeons. A copy of the written IRB-approved informed consent will be provided. Because Feraheme®-based imaging is in use at several pediatric specialty centers, including UCLA whereby Feraheme is used more frequently than GBCA-based imaging for children in our study age-group, in the current state of professional equipoise, we judge it appropriate to allow parents to participate in the choice of agent (see Section 11.1.1 for detailed justification). Those choosing to undergo an Ablavar®-enhanced MRI will be considered the "control" group while those choosing to undergo a Feraheme®-enhanced MRI will be considered enrolled in the "test" group. We plan to recruit 40 patients for test group and 40 patients for the control group with consideration of approximately 10% missing or unusable image quality. To avoid performing a study with larger-than-necessary enrollment, the Investigators will request an interim analysis at 50% enrollment for both groups. If statistical analyses, either as part of interim analyses requested by the Investigators, or after full enrollment, shows statistically significant primary endpoint comparison, we will close Part I enrollment and begin Part II enrollment using the superior agent identified in Part I. If statistical significance is not reached for the primary endpoint during interim analyses, the patient enrollment for both test and control groups will continue until full enrollment, at which time another final statistical analyses will be performed with $p < 0.025$ considered statistically significant. If statistical significance is not reached at full enrollment, we will seek advice from the DMC regarding Part II of the study, including contrast agent to be used.

See Section 11.1.1 for justification for involving the patient's parents in patient group assignment.

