18.1 Data Sets Analyzed

All eligible patients who receive Feraheme or Ablavar infusion as part of our study will be included in the data analysis. The results will be reported separately for the two contrast agents.

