18.3 Definition of Numeric Efficacy Outcomes

Subjective Image Quality Scores: The image quality will be independently scored by 2 board certified blinded readers with >5 years of cardiovascular MRI reading experience using a 1-4 point scale (1). The composite image quality score for each subject will be a number between 7 (all subjective image quality scores are 1=non-diagnostic) to 28 (all subjective image quality scores are 4=clear visualization). The scores will be assessed separately for each of the following seven anatomical structures that are important for imaging pediatric CHD patients: the aortic root, the pulmonary artery (PA), the coronary arteries, the out-flow tracts, the valves, the ventricles, and the atria. If the difference in the composite score is greater than or equal to 4 between two image readers, the readers will read the image together in a consensus reading session and arrive at a consensus for each of the 7 structures. The criteria for assigning scores will be as follows: 1) For **aortic root and PA**, 1=nondiagnostic (vessels not visualized or diagnostically not assessable due to small size and /or motion artifact and /or poor contrast enhancement), 2=vessels visualized but with poor contrast enhancement and /or motion artifact so as to limit confident assessment and measurement of dimensions, 3=vessels visualized with good contrast so as to enable confident assessment of patency but with poor edge definition due to motion artifact so as to limit confident measurement of dimensions, 4=vessels visualized with good contrast and good edge definition such that patency and dimensions are confidently assessable; 2) For **coronary arteries**: 1=nondiagnostic (vessels not visualized or diagnostically not assessable due to small size and /or motion artifact and /or poor contrast enhancement), 2=only origins of main coronary arteries confidently identifiable, 3=origins and proximal course of RCA and left anterior descending (LAD) confidently evaluable, 4=origin, proximal and mid courses of RCA and LAD and proximal takeoff of left circumflex confidently evaluable; 3) For **out-flow tracts and valves**: 1=nondiagnostic (structures not visualized or diagnostically not assessable due to small size and /or motion artifact and /or poor contrast enhancement, 2=annulus and sinotubular junction visualized but borders not sufficiently well defined for confident measurement, 3=annulus and sinotubular junction visualized with well defined borders sufficient for confident measurement, 4=annulus and sinotubular junction clearly visualized with well defined borders sufficient for confident measurement and valve leaflets clearly seen; 4) For the **ventricles and atria**: 1=nondiagnostic (chambers not visualized or diagnostically not assessable due to small size and /or motion artifact and /or poor contrast enhancement, 2=chambers distinguishable but walls poorly defined and only gross features evaluable, 3=chambers clearly distinguishable with well defined septum and free walls confidently evaluable but with poor definition of the papillary

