18.4 Primary Efficacy Endpoints

18.4.1 Part I – Difference in the composite image quality score between Feraheme and Ablavar

The primary efficacy endpoint for Part I is the composite image quality score, which is defined as the sum of the subject image quality scores assigned to seven important anatomical structures for pediatric CHD patients: the aortic root, the PA, the coronary arteries, the outflow tracts, the valves, the ventricles, and the atria. The score will be the average scores from all the image readers. The consensus reading will occur if the difference in the composite score from the same image is 4 or greater. The composite image quality score will be tested for normality using the Shapiro-Wilk and Shapiro-Francia tests. For normally distributed data, comparison will be made between the composite image quality scores for Feraheme and Ablavar using a parametric two-sided t-test with an appropriate transformation if needed. If statistical transformation of the image quality score is not possible, a non-parametric Wilcoxon-rank-sum test can be considered. The null hypothesis is that there is no difference in the composite subjective image quality scores between Feraheme and Ablavar. This comparison will be a two-sided test at the overall 0.05 level of significance. Summary statistics of mean, standard deviation and their 95% confidence intervals of each contrast agent and the difference will be used for statistical description. There will be a formal interim analysis and a primary analysis for image quality score. The primary analysis of image quality scores will be performed when 80 CHD subjects are enrolled and the images are scored by the image readers. Scores for subjective image quality, sharpness and CNR measurements will remain blinded from the Investigators and only the study statistician will be able to pair the contrast assignment and the score.

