18.7 Sample Size and Power Estimate for the Primary Efficacy Endpoints

18.7.1 Part I – Difference in the composite image quality score between Feraheme and Ablavar

Sample size and power estimates are based on data from an internal pilot analysis. Based on the average composite image quality scores of two independent readers, the mean image quality score was 25.62 with a standard deviation of 1.82 for the Feraheme-enhanced, ventilator-gated MUSIC-MRI group. The difference in the image quality scores between two readers was a mean of -1.96 with a standard deviation of 2.72. We expect the agreement between two independent readings will improve with consensus reading in cases with largely different image quality scores (4 or more absolute difference in the score).

Based on the above preliminary analyses, for the interim analysis, a sample size of 20 in each contrast agent group will achieve a power of 62% to detect a difference of 1.75 (7% reduction) in the composite image quality scores between the Ablavar group and the Feraheme group with an estimated standard deviation of 2.10 in each group and a significance level of 2.5%.

In the primary analysis, a sample size of 36 subjects will achieve a power of 90% to detect a difference of 1.75 (7% reduction) in composite image quality scores between the Ablavar group and the Feraheme group with an estimated standard deviation of 2.10 in each arm and a significance level of 2.5%. Taking into consideration missing data due to unusable image quality or incomplete studies, we plan to enroll 40 CHD subjects in each group (N=80).

18.7.2 Part II – Difference in the composite image quality score between ventilator-gated and self-gated MUSIC-MRI

The quality of self-gated images are expected to be of at least equal quality to ventilator-gated images with a larger standard deviation due to variation in the methods of respiratory motion gating. We choose the non-inferior margin (87) to ensure that the upper bound of the 95% confidence interval (CI) for the difference between ventilator-gated and self-gated (ventilator – self-gated) is less than 1.75. We expect the mean of the composite image quality score for ventilator-gated images to be approximately 25.62, which is the expected upper limit of the self-gated image quality

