score. The margin of 1.75 was derived using an expected mean of 24.75 for the self-gated image (~4% reduction in image quality score compared to that achieved with the ventilator-gated method). The non-inferiority comparison will be a one-sided test at a 0.025 level of statistical significance and a -1.75 margin. A sample size of 36 will achieve a statistical power of greater than 90% to detect non-inferiority between ventilator-gated and self-gated MUSIC-MRI using a one-sided t-test with a non-inferiority margin of -1.75 and a true difference of zero with a standard deviation of 3.0 and a significance level of 2.5%. Taking into account missing data due to unusable image quality or incomplete studies, we plan to enroll 40 CHD subjects.

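### Section 18 limits the primary image-quality analysis to undefined usable scans, so the endpoint's worst scores can drop out although 18.3 gives them a value and 18.1 includes every eligible infused child

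*Combined protocol and SAP*

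**What the plan says.** Five places bear on which scans enter the primary analysis.

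- **Section 18, opening paragraph:** "The primary efficacy analysis of visual imaging quality will be conducted using all usable scans from the patients". Usable has no criterion, no named assessor and no blinding rule.
- **Sample size.** 18.7.1 raises 36 to 40 per group: "Taking into consideration missing data due to unusable image quality or incomplete studies". 18.7.2 does the same for Part II: "Taking into account missing data due to unusable image quality or incomplete studies, we plan to enroll 40 CHD subjects". Section 7.2 describes Part I enrolment as set "with consideration of approximately 10% missing or unusable image quality". In 18.7 poor image quality is a kind of missing data, listed apart from incomplete studies.
- **Section 18.3:** for the aortic root and pulmonary artery, score 1 covers "vessels not visualized or diagnostically not assessable due to small size and /or motion artifact and /or poor contrast enhancement"; the other structures have a matching lowest category. Also: "The composite image quality score for each subject will be a number between 7" (every structure non-diagnostic) and 28.
- **Section 18.1:** "All eligible patients who receive Feraheme or Ablavar infusion as part of our study will be included in the data analysis". There is no exception for quality.
- **Section 18.4.1:** the Part I primary analysis takes place "when 80 CHD subjects are enrolled and the images are scored by the image readers", with no usability filter.

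Section 11.2 blinds the readers to agent (Part I) and technique (Part II) and lets only the study statistician pair assignment with score. Section 15.3 replaces children who withdraw before images are recorded; it does not cover poor images.

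**The concern.** On this scale a failed image is an outcome. A scan ruined by motion or weak enhancement is what the composite score is meant to penalise, and 18.3 gives it a number. Section 18 is the sentence specific to the primary image-quality analysis, and it allows that scan to be removed.

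If failures are equally frequent in the two groups, little bias follows. If they differ, the analysis compares only the successes of each agent or technique. In Part II, dropping self-gated failures favours non-inferiority. In Part I, dropping failed Ablavar scans hides a Feraheme advantage, and dropping failed Feraheme scans exaggerates one.

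The direction cannot be known from the documents. The self-gated sequence is still to be developed (7.3) and is expected to have a larger standard deviation (18.7.2). But 18.7.2 also expects at least equal quality, and 7.3 expects a shorter acquisition and better gating. Failures common to both techniques in the same child, such as inadequate sedation (4.3), largely cancel in the paired comparison.

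**Working it through.** **The plan's own figures reproduce.** Inputs (18.7.1): difference 1.75, SD 2.10, two-sided 0.025, power 90%.

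n = 2 × (2.10/1.75)² × (2.241 + 1.282)² = 2 × 1.44 × 12.41 = 35.7, so 36 per group. Power by the noncentral t is 0.891 at 36 and 0.923 at 40; at the interim (20 per group) it is 0.620, as stated. 36/(1 − 0.10) = 40. For Part II (margin −1.75, SD 3.0, one-sided 0.025, true difference 0), power is 0.925 at 36 and 0.949 at 40. The sample-size arithmetic is sound; the problem is the analysis set.

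**Assumptions.** Failure rates and failed-scan scores are mine. I take failed composites of 7 (the floor) to 14 and rates of 2.5% to 10%. The pilot mean 25.62 and SD 1.82 come from 18.7.1.

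**Part II, one self-gated-only failure in 40.** The failed pair is score − 25.62; the other 39 pairs have mean 0, SD 3.0.

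- Dropped (n = 39): 95% lower bound −0.97.
- Scored 7: mean −18.62/40 = −0.466, SD 4.18, bound −0.466 − 2.023 × 4.18/√40 = −1.80.
- Scored 14: mean −0.291, SD 3.48, bound −1.41.

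By t-test, one exclusion can move the bound across −1.75, but only when the failed scan scores at the floor; at 8 the bound is −1.74.

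**Part II, share of simulated trials declaring non-inferiority** (40 children; ventilator score normal, 25.62, SD 1.82; other paired differences normal, 0, SD 3.0). Ranges run over failed scores 7 to 14.

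| Self-gated-only failures | Usable-only | All scored, t-test | All scored, Wilcoxon signed-rank |
|---|---|---|---|
| 2.5% | about 95% | 52-72% | about 85% |
| 5% | about 94% | 25-49% | 69-70% |
| 10% | about 92% | 5-17% | 36-38% |

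The true mean difference reaches the margin when the failure rate equals 1.75/(25.62 − score): 1.75/18.62 = 9.4% for score 7, and 1.75/11.62 = 15.1% for score 14. At 10% scored 7 it is 0.10 × (7 − 25.62) = −1.86, past the margin, and usable-only still declares non-inferiority in about 92%.

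**Part I** (40 per arm, SD 2.10, two-sided 0.025).

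- *10% Feraheme-only failures, 1.75 advantage among usable scans.* Feraheme all-scan mean, scored 7: 0.9 × 25.62 + 0.1 × 7 = 23.76, against 23.87 for Ablavar, a difference of −0.11 (0.59 if scored 14). Feraheme is found superior in about 91% usable-only, against 4-11% (t-test) or about 53% (Wilcoxon rank-sum) with all scans scored.
- *10% Ablavar-only failures, no difference among usable scans.* The all-scan difference is 0.10 × 18.62 = 1.86 (scored 7) or 0.10 × 11.62 = 1.16 (scored 14). Usable-only detects it at about the nominal 2.5%, against roughly 22-28% (t-test) or 7% (Wilcoxon) if scored.

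**The case against.** **The t-test figures overstate the effect.** Section 18.4 calls for normality tests and, if transformation is not possible, a Wilcoxon test may be considered. Composites of 7 among scores near 25.6 would trigger that: in Part II, Shapiro-Wilk rejects in over 99% of trials with at least one failure scored 7, and in 54-85% when scored 14. This stands, and the Wilcoxon column belongs beside the t-test column. A clear gap to usable-only remains at 5% and 10%. The fallback wording is permissive, so neither column is certain.

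**The scenarios are severe.** A composite of 7 needs all seven structures non-diagnostic, about ten pilot SDs below the mean: (25.62 − 7)/1.82 = 10.2. The 10% in 7.2 covers missing and unusable images together, and the scenarios above place failures in one arm or technique only. This stands as a limit on size.

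**Every child may be meant to be scored.** The sentences in 7.2 and 18.7 are enrolment allowances, and 18.3 and 18.4.1 read as if every child has a score. Part of the defect is therefore text that does not agree. But usable could mean acquisition completed only if the plan said so, and 18.7 lists poor quality separately from incomplete studies.

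**A reader might infer that exclusions will be made unblinded**, because the synopsis says investigators see assignment and images in Part I. The documents do not support that. Section 11.2 blinds the readers, and no section gives investigators the usability decision. What can be said is that nobody is named and blinding of this decision is not stated.

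**Conclusion.** The concern holds as an undefined analysis set that conflicts with the plan's own scoring rule and data-set definition. As written, section 18 permits the lowest endpoint values to leave the primary analysis of both parts, and the result is biased if failures differ by agent or technique.

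The size is conditional on assumed failure rates and scores. At 2.5% self-gated-only failures the true difference is still well inside the margin, so the harm is overstated certainty: about 95% of trials declare non-inferiority, against 85% (Wilcoxon) or 52-72% (t-test). A false non-inferiority conclusion on the mean scale needs rates above roughly 9-15%, depending on the failed score. Where all failures are shared by both techniques, the problem largely disappears.

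A reader might go further and conclude that the trial is set up to reach a false non-inferiority finding, or that it favours Feraheme. The documents support neither: they give no failure rate by agent or technique, and the direction in Part I is open. The point should still be fixed, before any score is unblinded, because a later choice of analysis set would be post hoc.

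**What to change.** Align 18, 18.1 and 18.4 as follows.

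1. The blinded readers score every acquired MUSIC scan on the 18.3 scale, with non-diagnostic structures scored 1.
2. Only scans that were never acquired count as missing. The reason is recorded, and classified before scores are unblinded by someone blind to agent or technique.
3. Acquisitions abandoned for image quality or gating failure enter a worst-score sensitivity analysis.
4. Before scoring, fix which acquisition counts when a scan is repeated (4.3 expects repeats). The rule must not discard a poor first scan on quality; taking the last completed acquisition, for instance, could do so.
5. State in advance that the rank-based test in 18.4 is used if failed scans make the scores non-normal.
6. Keep usable-only as a sensitivity analysis, with usable defined and judged blind. Report failures and repeats by agent and technique.

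The change is wording; readers, scale and scans stay the same. The cost is power, because failed scans widen the distribution. With 2.5% failures in both arms, Part I falls from about 92% to 86-87% by Wilcoxon, or 53-70% by t-test. Power should be restated over a range of failure rates and scores.

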18.1 Data Sets Analyzed

All eligible patients who receive Feraheme or Ablavar infusion as part of our study will be included in the data analysis. The results will be reported separately for the two contrast agents.

